#### **5.4.2.3. Distribution of percentages of serogroup B invasive disease strains killed**

Not applicable

#### **5.4.2.4. Immune response of MenABCWY, rMenB+OMV NZ and MenACWY**

Not applicable

### **5.5. Safety and reactogenicity**

#### **5.5.1. Analysis of safety and reactogenicity planned in the protocol**

Distribution of subjects by vaccinations will be summarised by vaccine group for the Enrolled Set. In case of vaccination error, subjects will be analyzed “as treated” (according to the vaccine the subject received).

**Analysis sets:** Solicited Safety Set (solicited local and systemic adverse events and other solicited adverse events), Unsolicited Safety Set (unsolicited adverse events), and Overall Safety Set.

**CONFIDENTIAL**

205416 [MENB REC 2ND GEN-038 (V72\_72)]

Statistical Analysis Plan Amendment 9

Endpoint	Statistical Analysis Methods
Primary	
Endpoints description: The frequencies and percentages of subjects with solicited local (i.e., injection site pain, erythema, swelling, induration) and systemic (i.e., fever [temperature <math>\geq 38.0^{\circ}\text{C}</math>], nausea, fatigue, myalgia, arthralgia, headache) adverse events during the 7 days (including the day of vaccination) following each vaccination at Day 1, Day 61 and Day 181.
 
All solicited adverse events will be summarised according to defined severity grading scales, see protocol section 12.5.9.3.
 
Frequencies and percentages of subjects experiencing each adverse event will be presented for each symptom severity. Summary tables showing the occurrence of any local or systemic adverse event overall and at each time point will also be presented.
 
Post-vaccination solicited adverse events reported from Day 1 to Day 7 will be summarised for the intervals Day 1-3, Day 4-7, and Day 1-7 by maximal severity and by vaccine group, excluding the 30-minute measurement, which will be summarised separately. The severity of solicited local adverse events, including redness (erythema) at injection site, swelling of skin at injection site, and hardness of skin at injection site will be summarised according to categories based on linear measurement: None (1 to 24mm); Mild (25 to 50mm); Moderate (51 to 100mm); Severe (<math>>100\text{mm}</math>).
 
Injection site tenderness and systemic reactions (except fever) occurring up to 7 days after each vaccination at Day 1, Day 61 and Day 181 will be summarised according to "mild", "moderate" or "severe".
 
Each solicited local and systemic adverse event will also be further summarised as "none" versus "any" (for fever the latter will be <math>\geq 38.0^{\circ}\text{C}</math>).
 
Use of antipyretics and analgesics will be summarised by frequency by type of use (prophylactic versus treatment) and percentage of subjects reporting use.
 
Body temperature will be summarised by <math>0.5^{\circ}\text{C}</math> increments from <math>36.0^{\circ}\text{C}</math> up to <math>\geq 40^{\circ}\text{C}</math> and will be broken down according by route of measurement, if applicable. Frequencies and percentages of subjects with temperatures <math>\geq 38.0^{\circ}\text{C}</math> and temperatures <math>\geq 40.0^{\circ}\text{C}</math> will also be presented.

	
Endpoints description: The frequencies and percentages of subjects with any unsolicited AEs (including all SAEs), AEs leading to withdrawal and medically attended AEs during the 7 and the 30 days (including the day of vaccination) following each vaccination at Day 1, Day 61 and Day 181.
 
The frequencies and percentages of subjects with SAEs, AEs leading to withdrawal, AESIs and medically attended AEs throughout the study period.
 
This analysis applies to all adverse events occurring during the study, judged either as possibly related, or not related to vaccination by the investigator, recorded in AE CRF, with a start date on or after the date of first vaccination. AE starting prior to the first vaccination will only be listed.
 
The original verbatim terms used by investigators to identify adverse events in the CRFs will be mapped to preferred terms using the MedDRA dictionary. The adverse events will then be grouped by MedDRA preferred terms into frequency tables according to system organ class.
 
All reported adverse events, as well as adverse events judged by the investigator as possibly related to study vaccine, will be summarised according to system organ class and preferred term within system organ class. These summaries will be presented by vaccine group and by interval of study observation. When an adverse event occurs more than once for a subject, the maximal severity and strongest relationship to the vaccine group will be counted.
 
Separate summaries will be produced for the following categories:
 
 
• Serious adverse events.
 
• Adverse events that are possibly related to vaccine.
 
• Adverse events of special interest.
 
• Adverse event leading to withdrawal.
 
• Adverse events leading to a medically attended visit.
 
 
Data listings of all adverse events will be provided by subject. In addition, adverse events in the categories above will be provided as listed data.
 
Local and systemic AEs will be analyzed by point estimates with associated 95% CIs [Clopper, 1934].

### **5.5.2. Additional considerations**

For analyses of the safety and reactogenicity endpoints, subjects will be analyzed “as treated” according to the actual vaccination a subject received.

For participants who have more than one solicited local (i.e., injection site pain, erythema, swelling, induration) or systemic (i.e., fever [temperature  $\geq 38.0^{\circ}\text{C}$ ], nausea, fatigue, myalgia, arthralgia, headache) measurement on a day, all data is listed. For the analysis, the worst measurement is analyzed. For example, if for a participant a temperature of  $38.5^{\circ}\text{C}$  and  $39.0^{\circ}\text{C}$  is recorded on one day, both values get listed, for the analysis the  $39.0^{\circ}\text{C}$  is analyzed.

Analyses of safety objectives will be repeated by age group (10-17 years of age and 18-25 years of age), race, sex, region (US/ ex-US), and with and without a previous MenACWY vaccination (primed and unprimed).

[figure not shown]
A Table and Listing of COVID-19 AE cases will be provided.

In case for a subject besides ediary data, also solicited reactions were recorded in the CRF, the CRF data will be mapped into the SDTM data with the ediary data (FA domain). For the analysis, the CRF data will be used in case of duplicate data.

## **6. ANALYSIS INTERPRETATION**

Multiple objectives and endpoints require type I error control. Full alpha (0.05) is split equally (alpha=0.025) between rMenB+OMV NZ objectives and MenABCWY objectives. Furthermore, within rMenB+OMV NZ, as well as within MenABCWY, objectives are tested hierarchically. If the first null hypothesis is rejected, then the testing will continue with the second hypothesis at same alpha. Same for 3rd, 4th, and so forth. Whenever a null hypothesis is not rejected, then the testing will stop.

As the comparator for MenABCWY non inferiority objective for the B component will be the selected schedule of rMenB+OMV NZ as determined in this study, the objectives of rMenB+OMV NZ will be analysed first. Additionally, if all null hypotheses related to rMenB+OMV NZ objectives will be rejected, the alpha (alpha=0.025) will be propagated to the MenABCWY part, and hypotheses related to MenABCWY objectives will be tested at full alpha (alpha=0.05). See [Figure 2](#) for an explanation of the hierarchical testing (top to bottom, the order indicated by the arrows).

**Figure 2** Hierarchical testing of hypothesis

\* Alpha split equally between rMenB+OMV NZ and MenABCWY vaccine objectives.

If all rMenB+OMV NZ objectives achieved, MenABCWY vaccine objectives will be tested at full alpha.

\*\* If all objectives of rMenB+OMV NZ are met, the comparator will be the 0,2-months schedule. If the 0,2-months objective is not met, and the 0,6-months is met, then the 0,6-months schedule will be the comparator. If the 0,6-months is also not met, then the 0,2,6-months schedule will be the comparator.

Refer to [Glossary of terms](#) for definitions of test-based and responder-based vaccine effectiveness.

## 7. CONDUCT OF ANALYSES

### 7.1. Sequence of analyses

The final study report will contain at least the final analyses of all primary and secondary endpoints.

### 7.2. Statistical considerations for interim analyses

No interim analysis is planned for this study

## **8. CHANGES FROM PLANNED ANALYSES**

Not applicable

## **9. NON-STANDARD DATA DERIVATION RULES AND STATISTICAL METHODS**

The following sections describe additional derivation rules and statistical methods which are not presented in section 10.1.

### **9.1. Data derivation**

Not applicable

### **9.2. Statistical Method**

Not applicable

## **10. ANNEXES**

### **10.1. Business rules for standard data derivations and statistical methods**

This section contains GSK Vaccines' standard rules for data display and derivation for clinical and epidemiological studies.

#### **10.1.1. Attributing events to vaccine doses**

The dose relative to an event is the most recent study dose given to a subject prior to the start of a given event. For example, if the start date of an adverse event is between Dose 1 and Dose 2, the relative dose will be Dose 1.

If an event starts on the same day as a study dose, the relative dose will be derived from the additional information provided in the CRF using the contents of the flag indicating if the event occurred before or after vaccination. If 'after vaccination' is selected, the relative dose for the event will be the one administered on the start day of the event. If 'before vaccination' is selected, the relative dose for the event will be the dose prior to this one.

#### **10.1.2. Handling of missing data**

##### **10.1.2.1. Dates**

When partially completed dates (i.e. with missing day or month) are used in calculations, the following standard rules will be applied:

- A missing day will be replaced by 15

- A missing day and month will be replaced by June 30th.

The following exceptions apply:

- Adverse event start dates with missing day:
  - If the event starts in the same month as at least one of the study doses, the contents of AE.AESTRTPT (the flag indicating if the event occurred before or after vaccination) will be used to complete the date. If ‘after vaccination’ is selected, the imputed start date will match the first (or only) study dose given during that month. If ‘before vaccination’ is selected, the imputed date will be one day before the first (or only) study dose given during that month.
- Adverse event start dates with missing day and month:
  - If the event starts in the same year as at least one of the study doses, the contents of AE.AESTRTPT (the flag indicating if the event occurred before or after vaccination) will be used to complete the date. If ‘after vaccination’ is selected, the imputed start date will match the first (or only) study dose given during that year. If ‘before vaccination’ is selected, the imputed date will be one day before the first (or only) study dose given during that year.

All other cases of incomplete AE or concomitant medication/vaccination start date will follow the standard rules above.

#### **10.1.2.2. Laboratory data**

Missing laboratory results (including immunological data) will not be replaced.

#### **10.1.2.3. Daily recording of solicited adverse events**

##### **10.1.2.3.1. Studies with electronic diaries**

For studies using electronic diaries for the collection of solicited adverse events, a solicited adverse events will be considered present only when a daily recording of grade 1 or more is present.

#### **10.1.2.4. Unsolicited adverse events**

Unsolicited adverse event summaries are including serious adverse events unless specified otherwise.

Missing severity, relationship with study vaccine, and outcome of unsolicited adverse events will not be replaced and will appear as ‘UNKNOWN’ in all statistical output.

#### **10.1.3. Data derivation**

##### **10.1.3.1. Age at vaccination in days**

When age at vaccination is to be displayed in days, it will be calculated as:

Age = date of vaccination minus date of birth

**10.1.3.2. Age at vaccination in months**

When age at vaccination is to be displayed in months, it will be calculated as the number of complete calendar months between the date of birth (DOB) and the date of vaccination. For example:

DOB = 10JUN2017, Date of vaccination = 09JUL2018 -> Age = 12 months

DOB = 10JUN2017, Date of vaccination = 10JUL2018 -> Age = 13 months

**10.1.3.3. Age at vaccination in years**

When age at vaccination is to be displayed in years, it will be calculated as the number of complete calendar years between the date of birth and the date of vaccination. For example:

DOB = 10SEP1983, Date of vaccination = 09SEP2018 -> Age = 34 years

DOB = 10SEP1983, Date of vaccination = 10SEP2018 -> Age = 35 years

**10.1.3.4. Weight**

Weight will be presented in kilograms. Weights reported in pounds will be converted as follows:

Weight in kilograms = Weight in pounds / 2.2

**10.1.3.5. Height**

Height will be presented in centimeters. Heights reported in feet and inches will be converted as follows:

Height in centimeters = Height in inches x 2.54

**10.1.3.6. Body mass index (BMI)**

BMI will be calculated as follows:

BMI = (Weight in kilograms) / (Height in meters)

**10.1.3.7. Temperature**

Temperatures will be presented in degrees Celsius (°C). Temperatures reported in degrees Fahrenheit (°F) will be converted as follows:

Temperature (Celsius) = ((Temperature (Fahrenheit) - 32) x 5)/9

### 10.1.3.8. Numerical serology results

Numerical serology results will be derived from the content of IS.ISORRES in the SDTM dataset. For assays with a specific cut-off, the following derivation rules apply:

IS.ISORRES	Derived value
“NEG”, “-”, or “(-)”	cut-off/2
“POS”, “+”, or “(+)”	cut-off
“< value” and value is <= assay cut-off	cut-off/2
“< value” and value is > assay cut-off	value
“> value” and value is < assay cut-off	cut-off/2
“> value” and value is >= assay cut-off	value
“value” and value is < cut-off	cut-off/2
“value” and value is >= cut-off	value
All other cases	missing

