#### **5.3.1.8. Immunological non-inferiority: MenABCWY vs. MenACWY**

Analysis set: PPS restricted to subjects without previous ACWY vaccination will be the primary analysis population.

Statistical method: The percentage of subjects with 4-fold rise\*P in hSBA titres against MenACWY indicator strains A, C, W and Y and the corresponding exact two-sided 97.5% CIs based on Clopper-Pearson method will be calculated for the ABCWY (pooled lots) group and the ACWY group [[Clopper, 1934](#)]. The 97.5% CIs for the difference in percentages between ABCWY (pooled lots) and ACWY group will be constructed using the method of Miettinen and Nurminen [[Miettinen, 1985](#)].

Non-Inferiority criterion: Non-inferiority of MenABCWY vaccine for the proportion of subjects with 4-fold rise will be demonstrated if the lower limit of the two-sided 97.5% CI for the difference in percentage of subjects with 4-fold rise between the 2 groups (ABCWY (pooled) lots –ACWY) is above -10%.

\* For the Men A, C, W, Y evaluation, the 4-fold rise is defined as:

- a post-vaccination hSBA titre  $\geq 4$  times the LOD or  $\geq$ LLOQ, whichever is greater, for subjects with a pre-vaccination hSBA titre  $<$ LOD
- a post-vaccination hSBA titre  $\geq 4$  times the LLOQ for subjects with a pre-vaccination hSBA titre  $\geq$ LOD but  $<$ LLOQ, and
- a post-vaccination hSBA titre  $\geq 4$  times the pre-vaccination titre for subjects with a pre-vaccination hSBA titre  $\geq$ LLOQ.

[Table 5](#) reads the LOD and LLOQ of MenACWY indicator strains used in the definition of 4-fold rise provided by the laboratory.

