**Table 5 LOD, LLOQ, and ULOQ of MenACWY indicator strains**

Strain	LOD	LLOQ	ULOQ
Men A (3125)	CC1		
Men C (C11)			
Men W (240070)			
Men Y (860800)			

If the co-primary effectiveness objectives for rMenB+OMV NZ are met (Sections 5.3.1.1 through 5.3.1.6), then the above will be evaluated at 95% CI.

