### 10.1.3.9. Geometric mean titres (GMTs) and concentrations (GMCs)

Geometric Mean Titre (GMT) or Concentration (GMC) calculations are performed by taking the inverse logarithm of the mean of the log titre or concentration transformations. Antibody titres or concentrations below the cut-off of the assay will be given an arbitrary value of half the cut-off of the assay for the purpose of GMT/GMC calculation. The cut-off value is defined by the laboratory before the analysis and is described in the protocol.

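### Section 10.1.3.8 of the SAP replaces some censored serology results with values the assay did not establish, so a sample reported as `<16` can be counted as reaching 16

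*SAP*

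**What the plan says.** SAP (Amendment 9) section 10.1.3.8 opens its table with "For assays with a specific cut-off, the following derivation rules apply". Two rows matter here:

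- A result of the type "< value” and value is > assay cut-off" is derived as the value.
- A result reported as above a value that is itself below the cut-off is derived as cut-off/2.

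Section 10.1.3.9 adds, for GMT and GMC calculation: "Antibody titres or concentrations below the cut-off of the assay will be given an arbitrary value of half the cut-off of the assay". On the cut-off itself it says: "The cut-off value is defined by the laboratory before the analysis and is described in the protocol".

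The section for study-specific derivations, 9.1, reads "Not applicable". Neither the 4-fold-rise sections (5.3.1.8, 5.4.1.1) nor the GMT sections (5.3.1.7, 5.4.1.4) make an exception for these results.

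The derived titres feed the primary comparison in section 5.3.1.8. There, for a baseline below LOD, the post-vaccination titre must reach 4 times LOD or LLOQ, "whichever is greater, for subjects with a pre-vaccination hSBA titre" below LOD. Non-inferiority requires that the lower limit for "ABCWY (pooled) lots –ACWY) is above -10"%.

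**The concern.** A result of `<16` says only that the titre is below 16. Assigning 16 picks the one number that the result rules out, and that number always lies above the cut-off. After vaccination, the sample can then be classed as a responder although its titre may be negative. At baseline, the assigned number raises the titre that the subject must later reach, and a true responder can be lost. The mirror row turns a result that may be positive into a value below the cut-off.

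The rule also sits badly with section 10.1.3.9. A sample whose true titre is below the cut-off should enter a GMT at half the cut-off, but if it was reported as `<16` it enters at 16.

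At stake are the A/C/W/Y 4-fold rise (primary, section 5.3.1.8), the serogroup B 4-fold rise and the percentages at or above LLOQ (secondary, sections 5.4.1.1 and 5.4.1.4), and the GMTs, including those for lot consistency (section 5.3.1.7).

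**Working it through.** The SAP gives no figure of its own to reproduce on this point. The check applies the table to example results and then illustrates the size.

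**Inputs.** The entries of the table "LOD, LLOQ, and ULOQ of MenACWY indicator strains" are redacted, and the cut-off is left to the protocol. I therefore assume LOD 4, LLOQ 8 or 16, and a cut-off equal to LOD or to LLOQ. Section 3.3 gives 411 × 3 = 1233 evaluable MenABCWY subjects and 137 evaluable ACWY subjects.

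**Step 1, after vaccination, LOD 4 and LLOQ 8.** With a baseline below LOD the threshold is max(4 × 4, 8) = 16.
- `<16` is derived as 16 and counts as a rise. The result shows that the titre is below 16, so the subject is a non-riser.
- `<32` is derived as 32 and counts as a rise. The true titre could be below 4 or as high as just under 32, so the answer is indeterminate.

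**Step 2, percentage at or above LLOQ.** If the cut-off equals LLOQ, every `< value` result above the cut-off is counted as at or above LLOQ. If the cut-off equals LOD, only those with value ≥ LLOQ are. With LLOQ 16 and cut-off 4, `<8` becomes 8 and is not counted, but `<16` becomes 16 and is.

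**Step 3, baseline, LOD 4 and LLOQ 8.** `<32` is derived as 32, so the required post-vaccination titre is 4 × 32 = 128. A subject who reaches 64 is a non-riser under the rule, but would be a riser if the true baseline were below 4 (threshold 16). A post-vaccination titre of 128 or more is a rise whatever the baseline below 32; one below 16 is never a rise; from 16 up to 128 the answer is indeterminate.

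**Step 4, mirror row, cut-off 8.** A post-vaccination `>4` becomes 4 and is a non-responder, although the titre may be high. A baseline `>4` becomes 4, giving a threshold of 4 × 8 = 32; a true baseline of 64 would have required 256.

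**Step 5, effect on the primary lower limit.** Assume half of the evaluable subjects are unprimed (616 vs 68), with true 4-fold rise of 82% (MenABCWY) and 85% (ACWY). The Miettinen–Nurminen lower limit is the d that solves (p1 − p2 − d) / √{[q1(1 − q1)/n1 + q2(1 − q2)/n2] × N/(N − 1)} = z. Here q1 and q2 are the maximum-likelihood rates under q1 − q2 = d, N = n1 + n2, and z = 2.241 (two-sided 97.5% CI). If the affected 2% are a random sample of the arm, only the 18% who are non-risers can change: 0.02 × 0.18 = 0.36 points.

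| Scenario | MenABCWY | ACWY | Lower limit |
|---|---|---|---|
| No misclassification | 505/616 | 58/68 | −11.5% |
| 2% of MenABCWY shift, all true non-risers | 517/616 | 58/68 | −9.5% |
| 2% of MenABCWY affected, random sample | 507/616 | 58/68 | −11.2% |
| 2 points in both arms | 517/616 | 59/68 | −10.6% |

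Without rounding to whole subjects the four limits are −11.3%, −9.2%, −10.9% and −10.7%. If all 1233 and 137 subjects were unprimed, the limit would be −9.0% before any misclassification, and non-inferiority would hold either way.

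**Step 6, effect on GMTs.** If a fraction f of a lot's samples is set to r times cut-off/2, when cut-off/2 would have been right, the GMT is multiplied by r^f. For f = 5%: 4^0.05 = 1.07 and 32^0.05 = 1.19. For f = 1% and r = 4 to 32: 1.01 to 1.04. The equivalence interval in section 5.3.1.7 is 0.5 to 2.0.

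**The case against.** Section 10.1 is the sponsor's standard rule set and covers every result string that could occur. Nothing in the SAP shows that any assay in this trial reports a `< value` result above its cut-off, so the rows may never be used. The limits and the cut-off are not visible here, so every worked case is conditional. Both points stand. They limit the size of the problem, but they do not make the derivation correct when it is used.

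The objection also rightly blocks several stronger readings:

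- **That responder status at or above LLOQ is a primary endpoint.** It is secondary (Table 1 and section 5.4.1.4). LLOQ enters the primary analysis only through the definition of the 4-fold rise.
- **That the bias has a known direction.** A post-vaccination error can add a riser and a baseline error can remove one. The 4-fold rise uses both samples, so the net sign is unknown.
- **That the enc-hSBA effectiveness primaries are affected.** Section 5.4.1.5 describes that assay as qualitative, so they are probably untouched.
- **That every such result should simply be deleted.** Section 10.1.2.2 concerns missing results, whereas `<32` is an observed, censored one. Deletion would discard cases the bound settles, such as a baseline of `<32` with a post-vaccination titre of 512. It would also remove samples known to be below a bound, which can itself raise response rates and GMTs.

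**Conclusion.** The concern holds as a flaw in two rows of the derivation table. Where such results occur, the rule can credit a sample with a threshold that its own result excludes or leaves open. It can also raise a baseline beyond what was measured. No other part of the SAP corrects this.

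The likely effect is small, and its size cannot be computed from the SAP, because the frequency of such results is not given and the assay limits were assumed. A reader might infer that the primary non-inferiority decision is in danger. The documents do not support that. In the illustration the conclusion moved only when 2% of MenABCWY samples, all true non-risers, became risers with no shift in the ACWY arm. It did not move when the 2% was a random sample of that arm or when both arms shifted equally. The GMT effect is minor against the equivalence interval. This is a low-cost correction worth making, not a threat to the design.

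**What to change.** Rewrite the two rows of section 10.1.3.8 so that a censored result never counts as meeting a threshold its bound does not establish:

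1. For the 4-fold rise and for titres at or above LLOQ, classify from the bound where it settles the answer. Under the assumed limits, a post-vaccination `<16` against a threshold of 16 is a non-riser, and a baseline of `<32` with a post-vaccination titre of at least 128 is a riser.
2. Set the result to missing only where the bound leaves the answer open.
3. Run a sensitivity analysis with cut-off/2 for post-vaccination `< value` results above the cut-off, including for GMTs.
4. Report the number of such results by group and visit.

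The cost is two table rows and one derivation step in the SAP, plus a short count table. The downside is that a few indeterminate results are lost from the analysis. If the counts are zero, nothing changes.
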